Study Drug	Nitrous oxide (laughing gas). This is an FDA-approved general anesthetic and sedative agent used in hospitals and dentist offices. The use of nitrous oxide to treat bipolar depression is off-label and outside of the approved indication. Nitrous oxide will be administered under supervision of an attending-level anesthesiologist and according to standards set by the American Society of Anesthesiologists.
Intervention	Patients will receive a titrated mix of either 50% nitrous oxide/50% oxygen or "placebo" (50% nitrogen [inert]/50% oxygen) for 1 hour.
Study Design	Prospective, randomized, placebo-controlled trial using the Sequential Parallel Comparison Design. In the first stage , patients will receive 3 randomized 1-hour treatments of either nitrous oxide (25% patients) or placebo (nitrogen in air; 75% patients) every other day (e.g., M,W,F). In the second stage , participants assigned to placebo in Stage 1 will be randomized to three 1-hour treatments every other day (e.g., M,W,F) for one week, to either nitrous oxide (50% patients) or placebo (50% patients). Participants assigned to nitrous oxide in Stage 1 will remain on nitrous oxide in Stage 2. Assessments will be performed prior to each treatment series (baseline) and approximately 24 hours after inhalation sessions #1 and #2, and approximately 72 hours after inhalation session #3. One and two week assessments of continued efficacy will be made for exploratory evaluation, but not included in the primary efficacy analysis.
Inclusion and Exclusion Criteria	Inclusion Criteria Adults 18-75 years of age Treatment-resistant bipolar depressive disorder without psychosis and a MADRS baseline score of >20. All patients must have history of being on a serum-verified (at time of entry into study) mood stabilizer [lithium at 0.5-1.2mEq/L; or valproic acid, 50-125mcg/ml] or another mood stabilizer verified through medical records for 4 weeks prior to entry into the study and remain on this mood stabilizer during the course of the trial. Further, subjects will have failed two adequate dose/duration antidepressant courses in their lifetime, including one in the current depressive episode (verified by Antidepressant Treatment History Form). Good command of the English language Exclusion Criteria Schizophrenia Schizoaffective disorder Obsessive-compulsive disorder or panic disorder Active or recent substance abuse or dependence (in remission at least 1 year prior to the study; exception = nicotine use disorders) A diagnosis of personality disorder that may interfere with the patient's ability to improve on nitrous oxide as determined by study investigator Acute medical illness that may pose subject at risk during nitrous oxide administration (neurological disorders or medical disorders including dementia, stroke, encephalopathy, Parkinson's Disease, brain tumors, multiple sclerosis, seizure disorder, severe cardiac disease, any disease known to affect drug metabolism and excretion, i.e. renal or liver disease) per P.I. discretion Active suicidal intention (inability to contract for safety) Patients with significant pulmonary disease and/or requiring supplemental oxygen

	j) Contraindication against the use of nitrous oxide: pneumothorax; bowel obstruction; middle ear occlusion; elevated intracranial pressure; chronic cobalamin and/or folate deficiency treated with folic acid or vitamin B ₁₂ ; pregnant patients; breastfeeding women; previous administration of NMDA-receptor antagonists (e.g., ketamine); current electro-convulsive therapy treatment
Primary Outcome	Change in depressive symptoms on MADRS scale between baseline and day 7 follow-up
Measurements	a) MADRS; b) Ham-D17; c) Young Mania Rating Scale (YMRS); d) Profile of Mood States Brief, 2 nd edition (POMS 2); e) Quick Inventory of Depressive Symptoms-Self Report (QIDS –SR); f) Brief Psychiatric Rating Scale (BPRS); g) Scale for Suicidal Ideation (SSI); h) Clinician Administered Dissociative States Scale (CADSS)
Statistical Methodology	Comparison of scores on MADRS by repeated-measures mixed model

1. Specific Aims

- 1.1. To determine if nitrous oxide is an efficacious treatment for treatment-resistant bipolar depression.
- 1.2. To obtain data about the tolerability of nitrous oxide in this setting.

2. Background

Bipolar Disorder (BPD) is characterized by alternating periods of sustained elevation in mood (manic episodes) and decreased mood (depressive episodes) intermixed with euthymia. Historically, considerable research effort has been put towards treating the manic phase of BPD, while relatively little emphasis has been placed on the depressed phase of the illness (1, 2). While the emphasis has been on the manic phase of BPD, phenomenology studies of BPD demonstrate that the depressed phase predominates the overall time spent in mood dysregulation and is responsible for more psychosocial impairment (3, 4). Further, evidence demonstrates that a significant percentage (as high as 40%) of BPD patients suffering from the depressive phase are treatment resistant (5-7). In fact, meta-analyses suggest that in the depressed phase approximately 25% of BPD patients will respond to the addition of an adjunctive antidepressant (8).

Recently ketamine, an antagonist of the N-methyl-d-aspartate (NMDA) subtype of glutamate receptors, has been shown to produce a rapid antidepressant effect in patients with treatment-resistant unipolar depression after a single infusion of 0.5 mg/kg over 40 minutes (9-11). More recently, two studies have demonstrated similar antidepressant effects of ketamine in treatment resistant bipolar depression (12, 13).

Although these ketamine trials offer substantial promise in treating treatment-resistant bipolar depression, ketamine has several well-established side effects that may limit its clinical usefulness. These include dissociative symptoms, hallucinations, delusions, the possibility of precipitating mania in patients with BPD and significant sympathetic nervous system activation. In addition, administration of ketamine typically requires intravenous access and supervision by a physician experienced in sedation. These side effects render ketamine a less than ideal antidepressant, despite its favorable effects.

Preliminary Data

Nitrous oxide, commonly known as laughing gas, is the oldest and most commonly used anesthetic. It has a well-known safety profile and is widely and safely used as a sedative and analgesic by dentists. Similar to ketamine, nitrous oxide acts as an NMDA-receptor antagonist (14-16).

We hypothesized that nitrous oxide may have rapid antidepressant effects in patients with unipolar treatment-resistant major depression. In the first in-human, proof-of-principle, blinded, randomized placebo-controlled crossover trial (Nagele *et al.*, Biological Psychiatry, 2015), 20 unipolar TRD patients received a 1-hour inhalation of 50% nitrous oxide or placebo. We found that depressive symptoms improved significantly after receiving nitrous oxide compared to placebo (mean HDRS-21

change at 2 hours: -4.8 points, 95% CI -1.8 to -7.8 points, p= 0.002; at 24 hours: -5.5 points, 95% CI -2.5 to -8.5 points, p<0.001; comparison between nitrous oxide and placebo: p<0.001). Four patients (20%) had treatment response and three patients (15%) a full remission after nitrous oxide compared to one patient (5%) and none after placebo (odds ratio [OR] for response 4.0, 95% CI 0.45 – 35.79; OR for remission 3.0, 95% CI 0.31 – 28.8, respectively). No serious adverse events occurred and all adverse events were brief and of mild to moderate severity. These preliminary data strongly support our hypothesis that nitrous oxide will have antidepressant efficacy in patients with bipolar depression.

Over the course of the past seven years, we have established the Washington University Treatment-Resistant Depression Clinic headed by [name]. During this time, we have evaluated >125 patients with unipolar and bipolar treatment-resistant depression. Initial analyses of these data piqued our interest in the potential critical role of bipolarity in this population; we have observed that a large subset of treatment-refractory depression patients has significant family history of bipolarity (Conway et al., J Clin Psychiatry, 2015, in press), and of which a significant number may be responsive to nitrous oxide.

3. Drug Information

Nitrous oxide (laughing gas) is a colorless, odorless gas. Nitrous oxide is the oldest and most widely used FDA-approved anesthetic gas. The onset as well as offset of effect is within a few minutes. In this study we will use a mix of 50% nitrous oxide and 50% oxygen (nitrous) or 50% nitrogen/50% oxygen (placebo). This concentration (commonly used by dentists) avoids hypoxia and ideally achieves only mild to moderate sedation and is not sufficient to produce general anesthesia. Well-known side effects of nitrous oxide include: euphoria, sedation, nausea and vomiting, and inactivation of vitamin B₁₂ (commensurate with the duration of exposure and concentration used). Exposure to 50% nitrous oxide for 1 hour is considered extremely safe and has been well-tolerated in our preliminary studies. The use of nitrous oxide to treat treatment-resistant bipolar depression is off-label.

4. Eligibility

4.1. Inclusion Criteria

- a) Adults 18-75 years of age
- b) Treatment-resistant bipolar depressive disorder without psychosis and a Montgomery-Asberg Depression Rating Scale (MADRS) baseline score of >20. All patients must have history of being on a serum-verified (at time of entry into study) mood stabilizer [lithium at 0.5-1.2mEq/L; or valproic acid, 50-125mcg/ml] or another mood stabilizer verified through medical records for 4 weeks prior to entry into the study and remain on this mood stabilizer during the course of the trial. Further, subjects will also have failed two adequate dose/duration antidepressant courses in their lifetime, including one in the current depressive episode (verified by Antidepressant Treatment History Form).
- c) Good command of the English language

4.2. Exclusion Criteria

- a) Schizophrenia
- b) Schizoaffective disorder
- c) Obsessive-compulsive disorder or panic disorder
- d) Active or recent substance abuse or dependence (in remission at least 1 year prior to the study; exception = nicotine use disorders)
- e) A diagnosis of personality disorder (confirmed by patient interview and medical chart review) that may interfere with the patient's ability to improve on nitrous oxide as determined by study investigator
- f) Acute medical illness that may pose subject at risk during nitrous oxide administration (neurological disorders or medical disorders including dementia, stroke, encephalopathy Parkinson's Disease, brain tumors, multiple sclerosis, seizure disorder, severe cardiac disease,

any disease known to affect drug metabolism and excretion, i.e. renal or liver disease) per P.I. discretion

- g) Active suicidal intention (inability to contract for safety)
- h) Active psychotic symptoms
- i) Patients with significant pulmonary disease and/or requiring supplemental oxygen
- j) Contraindication against the use of nitrous oxide: pneumothorax; bowel obstruction; middle ear occlusion; elevated intracranial pressure; chronic cobalamin and/or folate deficiency treated with folic acid or vitamin B₁₂; pregnant patients; breastfeeding women; previous administration of NMDA-receptor antagonists (e.g., ketamine); current electroconvulsive therapy treatment

5. Enrollment

[figure not shown]
Patients with a diagnosis of bipolar depression and history of resistance to treatment (as defined above) will be recruited. Patients will be screened, consented for participation and enrolled in the study by study team personnel. We aim to recruit a total of 64 patients with the diagnosis of treatment-resistant bipolar depression, defined as failure to respond to two or more adequate dose-duration trials of antidepressant medications by history and chart verification.

6. Methods

6.1. Study Design (see summary figure below)

Prospective, randomized, placebo-controlled trial using the Sequential Parallel Comparison Design (SPCD) designed by PPD, a contract research organization. In the **first stage**, patients will be randomized (1:3 active [nitrous oxide] to placebo) to receive three 1-hour inhalation treatments every other day. Approximately 24-72 hours after the treatment session, patients will be assessed by the MADRS along with other scales as detailed below. Participants will also have follow-up visits/assessments performed approximately 1 and 2 weeks from the last inhalation session. The active treatment recipients from the **first stage** will receive a **second stage** of active treatment. All patients on placebo in the first stage (n \approx 48) will be re-randomized in the **second stage** (1:1 active to placebo) to three 1-hour treatments every other day, with the same follow-up visits/assessments as in Stage 1 (see study flow figure below). Throughout both stages group assignment will remain double-blinded to the participants and study raters conducting the assessments.

For ethical purposes, once the study blind has been broken those TRD subjects who were randomly assigned to receive successive placebo treatments will be offered an optional open label phase of active treatment (i.e., three 1-hour every other day inhalation treatments).

6.2. Randomization

The group assignment will be randomly assigned (1:3 active treatment to placebo) for each participant in Stage 1 and 1:1 (active: placebo) in Stage 2 for those previously assigned to placebo. Participants randomly assigned to active treatment in Stage 1 will remain on active treatment in Stage 2. PPD, LLC will be aiding in the randomization of participants. Study raters will remain blinded along with the participants to group assignment until the end of Stage 2. The team responsible for the administration of the nitrous oxide treatment and other study team members not conducting ratings will know the group assignment and can provide this information to participants or other team members if needed (see below for more information in 6.3).

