6.3. Blinding

Patients will be blinded to the group assignment. Nitrous oxide is a colorless and odorless gas which makes it unlikely for patients to identify the group assignment. Likewise, the study setup will be identical for both sessions, which will make an inadvertent unblinding of the study unlikely. The team responsible for the administration of the nitrous oxide treatment will be aware of the treatment assignment. This team is completely separate from the team assessing the study outcomes, which will be blinded to the group assignment. After the completion of each stage, patients will be asked to assess if they received active treatment or placebo using a Blinding Questionnaire. Responses will be recorded with a 5 point scale asking participants to rate the extent to which they knew they were exposed to nitrous oxide; 1) strongly believe the treatment was nitrous oxide, 2) somewhat believe the treatment was placebo, 4) strongly believe the treatment is placebo, and, 5) don't know.

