7.1. Follow-Up

Assessments will be performed before and after (approximately 1 and 24 hours) each treatment, with the exception of the 3rd inhalation treatments in each Stage which will be monitored at approximately 72 hours from last inhalation session. Additional follow-up visits will be scheduled approximately one and two weeks following completion of the final gas inhalation session in any study stage (to assess for lasting efficacy of nitrous effects). However, only the two 24 hour and one 72 hour measures will be used in the statistical analysis of efficacy. The one and two week assessments will be performed to obtain preliminary information regarding lasting efficacy.

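### Does the permission in section 6.2 to tell participants their assignment, with no disclosure rule in section 6.3, undermine the blind?

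*Combined protocol and SAP*

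**What the plan says.** Section 6.1 sets the rule for the whole trial: "Throughout both stages group assignment will remain double-blinded to the participants and study raters conducting the assessments". Section 6.2 repeats it: "Study raters will remain blinded along with the participants to group assignment until the end of Stage 2". The next sentence of 6.2 says who is not blinded. Besides the team giving the gas, "other study team members not conducting ratings will know the group assignment", and these people "can provide this information to participants or other team members if needed (see below for more information in 6.3").

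Section 6.3, to which the reader is sent, opens with "Patients will be blinded to the group assignment". It goes on: "The team responsible for the administration of the nitrous oxide treatment will be aware of the treatment assignment". It adds that this team is separate from the blinded outcome raters. It also plans a check on the blind: "After the completion of each stage, patients will be asked to assess if they received active treatment or placebo using a Blinding Questionnaire". It does not say when a participant may be told, who decides, or where this is written down.

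The blind is expected to be broken in one place only: 6.1 offers optional open-label treatment afterwards to those who had placebo in both stages. Section 8.1 refers to standard operating procedures that are not reproduced. Section 9 defines the full analysis set by randomization, dosing and a post-baseline assessment, without reference to whether a patient still is blinded.

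**The concern.** Participants are named outright as people who may be told, the only condition is need, and the cross-reference leads to no rule. Read alone, the sentence would let unblinded staff reveal an assignment in the middle of a stage.

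That would matter in three ways.

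- **Outcomes.** The QIDS-SR is completed by the patient, and a MADRS rating rests partly on what the patient reports. A blinded rater therefore does not fully protect either scale from a patient who knows the assignment.
- **The check on the blind.** The Blinding Questionnaire records belief. Without a record of disclosures, a told patient looks the same as one who guessed correctly.
- **The analysis.** Section 9 has no rule for ratings made after disclosure, so they would enter the MMRM like any others. A disclosure not noted at the time could be hard to reconstruct later.

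The arms are small, so each told patient would carry visible weight.

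**Working it through.** **Step 1. Set the passages side by side.**

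| Place | Participants | Raters | Staff giving gas, other non-raters |
|---|---|---|---|
| 6.1 | Blinded in both stages | Blinded in both stages | Not addressed |
| 6.2, first statement | Blinded to end of Stage 2 | Blinded to end of Stage 2 | Not addressed |
| 6.2, next sentence | May be told if there is need | Not named | Know the assignment |
| 6.3 | Blinded | Blinded, separate team | Gas team knows |

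Three sections state the participants' blind, and 6.1 and 6.2 give its duration. The permission comes straight after one of those statements. Taken as a free licence it would cancel the sentence before it. Taken as an exception it leaves all the passages consistent. The documents offer a use for it: somebody must identify the patients who had placebo twice so that they can be offered open-label treatment once the blind is broken. An exceptional need during a stage is the other natural use. The text does not spell out either limit, so this is a reading, though the only one under which the sections agree.

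The same reading settles the reference to other team members. Sections 6.1, 6.2, 6.3 and 7.2 all keep raters blinded, so the colleagues who may be told are not the raters.

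**Step 2. Which ratings could be touched.** Section 7.1 states that "only the two 24 hour and one 72 hour measures will be used in the statistical analysis of efficacy". That is at most three ratings per stage. A disclosure after the 72-hour rating of Stage 2, including one made for the open-label offer, touches none of them. A patient on nitrous oxide in Stage 1 stays on it and is outside the re-randomized Stage 2 comparison, so telling that patient during Stage 2 moves the Stage 2 contrast by zero.

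**Step 3. Size per told patient.** From the documents: 64 patients randomized 1:3, then 1:1 among those given placebo.

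- Stage 1 active: 64 × 1/4 = 16. Stage 1 placebo: 64 − 16 = 48.
- Stage 2, per arm: 48/2 = 24, before placebo responders are left out.

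The documents do not say how far being told would move a MADRS change. Assume b = 5 points, range 2 to 8. One told patient in an arm of size n moves that stage's contrast by b/n. This is an upper figure, because it takes the full shift at the time point analysed.

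| Told patient | n | b = 5 | b = 2 to 8 |
|---|---|---|---|
| Stage 1 active | 16 | 0.31 | 0.13 to 0.50 |
| Stage 2, either arm | 24 | 0.21 | 0.08 to 0.33 |
| Stage 1 placebo | 48 | 0.10 | 0.04 to 0.17 |

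Section 9 combines the stages with equal weights. It combines test statistics, so averaging the two contrasts is only an approximation. On that basis each figure halves: at b = 5, 0.16, 0.10 and 0.05. A 1-point shift in the combined contrast then needs 2n/b told patients, rounded up, all in one arm:

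- Stage 1 active: 2 × 16/5 = 6.4, so 7 of 16 (4 to 16 over the range of b).
- One Stage 2 arm: 2 × 24/5 = 9.6, so 10 of 24 (6 to 24).

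An exceptional-need clause would not be expected to produce such numbers.

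**Step 4. Would another analysis rule help?** The full analysis set keeps a told patient, as an all-randomized approach should. A rerun with later ratings set to missing would leave the primary result unchanged. It would also lean on missing-at-random where a disclosure may have followed an adverse event. With few told patients it would change little.

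**The case for a change.** The best case for a change is that the words mean what they say. Participants are listed as possible recipients, no limit is stated, and the pointer to 6.3 does not deliver one. The topics of the operating procedures listed in section 8.1 do not name unblinding. Section 9 also takes only placebo non-responders into the Stage 2 analysis, so a disclosure during Stage 1 could influence who counts as one. A written rule and a log would cost a few sentences and a sheet of paper.

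What stands is the gap in wording: 6.2 and 6.3 do not say when need arises or where a disclosure is noted.

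The rest goes further than the documents allow. They do not say that disclosures go unrecorded; they are silent. The unseen procedures on managing subjects and reporting adverse events could cover the matter. The pointer to 6.3 is not empty either, since that section says that the gas team knows the assignment and that the raters are kept apart from it. Nothing shows that disclosure during a stage is planned. The argument about responders, like the one about bias, needs several patients to be told early in a stage, against the stated blind.

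**Conclusion.** The wording is loose, but the design is not compromised. Read with 6.1, the rest of 6.2 and 6.3, the clause is an exception for unusual need or for the step after the blind is broken. Staff running the trial would apply it that way and would ordinarily note any disclosure. The primary analysis would be the same with or without a fuller rule.

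No overall effect can be computed, because the number told is unknown and may be zero. Per told patient it is 0.10 to 0.31 MADRS points on a stage contrast at an assumed 5-point shift, and about half that on the combined contrast. The conclusion rests on disclosure being rare during a stage and on raters staying blinded, as the plan states. It would need another look if disclosures during a stage turned out to be common, especially in the Stage 1 active arm.
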